#### 4.4. Per Protocol Population

The per protocol (PP) analysis set consists of all ITT subjects without major protocol deviation that will impact the efficacy analyses. Any ITT subjects who meet the following criteria will be excluded from the PP population:

- study treatment not received
- Week 40 visit not within 38 to 42 weeks from the Baseline visit
- not compliant to study drug dose regiment; treatment compliance <80% or >120%
- baseline dystrophin levels ██████████ predicted
- do not have a valid assessment of dystrophin levels at either Baseline or Week 40 visits

This analysis set will be used for supportive efficacy analyses.

#### 4.5. Safety Population

This analysis set will include all subjects who received at least one dose of ataluren and will be used for all safety summaries.

### 5. GENERAL CONSIDERATIONS

#### 5.1. Tables, Figures, and Listings

In general, continuous variables will be summarized using descriptive statistics including n (number of subjects), mean, standard deviation, median, minimum, and maximum. Categorical variables will be summarized using frequency count as number and percentage of subjects. Unless specified, all hypothesis testings are 1-sided at a 5% alpha level.

By subject data listings will be created for selected electronic case report form (CRF) domains sorted by subject and associated dates.

#### 5.2. Visit Window

Study day 1 (baseline) is defined as the date of the first dose of study drug during the treatment period. The nominal visit (ie, study visit captured on the CRF) will be used as the analysis visits in all efficacy analyses. For safety analyses, the unscheduled and Early Termination visits will be reclassified into analysis visits according to Table 2. If multiple visits occurred within the same visit window, the one closest to the target visit date will be used in the analysis. If two visits are equidistant to the target visit date, the latest will be used.

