### **6.5 Discontinuation of Study Intervention**

If after appropriate consideration of study drug interruption/modification and consultation with the PTC Therapeutics medical monitor, it is not appropriate for a subject to continue with study treatment, then study drug should be permanently discontinued. After permanent discontinuation of study drug for a safety concern, and if the initial event was reported as a SAE, then a follow-up SAE report form should be completed. In the case of a treatment discontinuation due to an event that is not an SAE, the PTC Therapeutics medical monitor should be notified (see Section 7.3). In addition, details regarding the reasons for discontinuation and the adverse events (AEs) leading to the discontinuation should be recorded in the source documents and in the appropriate CRF. The Early Termination Visit CRF should be completed and appropriate follow-up, ie, at ~4 weeks as per protocol or until recovery from or stabilization of the AE, whichever comes last.

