## 6.6 Participant Discontinuation/Withdrawal from the Study

All subjects who receive ataluren should remain in the study whenever possible. However:

- The parent/caregiver or legal guardian has the right to withdraw consent and discontinue ataluren at any time.
- If the subject's condition substantially worsens after initiating ataluren, the subject will be carefully evaluated by the Investigator. The subject will be withdrawn from treatment if continuing would place them at risk.
- The Investigator may withdraw the subject from ataluren, if, in the Investigator's clinical judgment, it is not in the subject's best interest to continue.
- Compliance will be evaluated at Visit 2, Visit 3, and at an early termination visit. Compliance is defined as a subject taking 80% to 120% of doses. In the event a subject becomes significantly noncompliant with ataluren administration, study procedures, or study requirements, the subject should be withdrawn from ataluren when the circumstances surrounding noncompliance increase risk to the subject or are anticipated to substantially compromise the interpretation of study results.
- If genotyping of the dystrophin gene indicates that patient does not carry a nonsense mutation in the gene.
- This study may be discontinued by the relevant regulatory authority, IRB/EC (Institutional Review Board/Ethics Committee), and/or PTC Therapeutics at any time.

The date ataluren is discontinued and the reason for discontinuation will be recorded in the source documents and in the electronic case report form (eCRF). The PTC medical monitor (or designee) should be informed via e-mail of when a subject discontinues study drug.

When ataluren is discontinued (regardless of the reason), the Investigator is expected to capture all the evaluations required at the end of study or follow-up and any additional evaluations should be completed that may be necessary to ensure that the subject is free of untoward effects. The subject should be encouraged to seek appropriate follow-up for any continuing health problems.

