Clinical Labs	X	X		X	X	X		For Visit 1, Visit 3, and unscheduled and early termination visits, subjects should fast approximately 8 hours prior to assessment. Biochemistry and other laboratory assessments will be analyzed by the central laboratory. Biochemistry, hematology, and urinalysis laboratory assessments. Creatine kinase will be assessed via the UV method or an equivalent method. At an unscheduled visit, clinical laboratory assessments will be done as necessary. At Visit 1 and Visit 3, clinical laboratory assessments should be performed prior to biopsy.
Height/Weight/BMI		X	X	X		X		Height (in cm) and weight (in kg) will be measured at Visit 1, Visit 2, and Visit 3-Early Termination. If the subject is unable to stand, sitting arm span and ulna length should be assessed as surrogate measurements for height.
Vitals (HR & BP)		X		X	X			Vital signs will include systolic and diastolic blood pressure, pulse rate, and body temperature. The pulse rate and blood pressure determinations will be performed with the subject in a sitting position after a 5-minute rest. Blood pressure will be measured in triplicate and the average will be recorded. Vitals should be taken prior to rNSAA and TFTs assessments and biopsy.
AE/SAE Monitoring	X	X	X	X	X	X	X	AEs must be assessed and documented at each clinic visit. Subjects, parents/caregiver or legal guardian will be encouraged to report AEs of concern at any time in the intervals between visits.
Concomitant medications	X	X	X	X	X	X		Concomitant medications will need to be collected starting 30 days prior to first dose of study drug.
Efficacy Assessments								
Muscle biopsy		X		X				If a subject received ≥6 months of therapy but early terminated, a biopsy may be performed if subject, parents or legal guardian agrees.
rNSAA		X		X				
TFTs		X		X				

Study Procedure	Screening  Week (visit window)	Visit 1  Baseline Week 1	Visit 2 Week 20 (± 14 days)	Visit 3 End of Study  Week 40 (± 14 days)	Unscheduled Visit	Early Termination 	Follow-up 	Notes
Pharmacokinetic Assessments								
PK blood sampling		X		X				PK samples will be drawn on Visit 1, samples will be drawn pre-first study dose and 2 hours postdose, and on Visit 3 will be drawn pre-morning dose and 2 hours postdose.
Study Drug Administration								

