### 7.1. Primary Efficacy Analyses

#### 7.1.1. Primary Analysis

The primary efficacy endpoint is the percent change from baseline in dystrophin levels (final concentration) following 40 weeks of ataluren therapy, as measured by ECL. The final concentration is calculated by dividing a sample's dystrophin concentration by its total protein concentration. In addition, the percentage of the predicted levels (% normal) will also be calculated as dystrophin levels normalized to dystrophin concentration of the control population ([Syneos Health Report No. 14597.051619.A](#)):

$$\% \text{ normal (in \%)} = 100 * \text{final concentration} / 33.8$$

Within each muscle location, the best, median, and the average of the dystrophin levels and the corresponding % normal values of the muscle cores will be summarized using descriptive statistics for each subject. In case any measured dystrophin concentrations are below the lower limit of quantification (LLOQ), the dystrophin concentrations will be set at 0.5\*LLOQ in the final concentration calculation for the statistical analysis.

The null hypothesis of the primary analysis is that the percent change from baseline in dystrophin levels following 40 weeks of ataluren therapy as measured by ECL is zero with the alternative hypothesis being that the change is greater than zero. To evaluate this hypothesis, a one-sided test at the 5% significance level will be employed.

The percent change from baseline at Week 40 in dystrophin levels measured by ECL will be analyzed using the mixed effect model repeated measurement (MMRM) analysis with factors of muscle locations, visits (baseline and Week 40) as fixed effects, and subjects as a random effect, based on ITT population. An unstructured covariance matrix will be used, and if the model fails to converge, then a compound symmetry matrix will be used. Since dystrophin level is known to be non-normally distributed, a log-transformation will be used in the analysis. The best dystrophin levels across all muscles are considered the primary analysis. A sample SAS code of the MMRM model is provided as follows:

```
proc mixed data = dataset;  
  
class subjid visit mlocation; /*mlocation is muscle location*/  
  
model lnaval = visit mlocation; /*lnaval is log-transformed dystrophin level*/  
  
random subjid;  
  
repeated visit / type = un;  
  
estimate "Week 40 change from baseline" visit -1 1;  
  
run;
```

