### 7.1.3. Sensitivity Analyses

The following analyses will be considered as sensitivity analyses:

- PP analysis: The same primary efficacy analysis described in Section 7.1.1 (Primary Analysis) will be repeated based on the PP population for the primary efficacy endpoint.
- The average and median dystrophin levels across all muscle locations based on the same method as described in Section 7.1.1 (Primary Analysis).
- Excluding subjects with baseline dystrophin levels [REDACTED] of the predicted levels: The same primary analysis described in Section 7.1.1 (Primary Analysis) will be repeated excluding subjects with baseline dystrophin levels [REDACTED] of the predicted levels. The same analysis on the average and median dystrophin levels across all muscle locations will also be repeated excluding such subjects.
- COVID-19 consideration: The Week 40 biopsy study day (defined as Week 40 biopsy date – first study drug date +1) will be added to the primary efficacy analysis model described in Section 7.1.1 (Primary Analysis) as a covariate. This analysis model will

be applied to the best, average, and median dystrophin levels analyses based on the ITT population.

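### Does the SAP need to say how an optional early-termination biopsy is labelled and whether it is analysed?

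*SAP*

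**What the plan says.** A note on the muscle biopsy row of the protocol's Schedule of Assessments reads: "If a subject received ≥6 months of therapy but early terminated, a biopsy may be performed if subject, parents or legal guardian agrees". The row itself is marked only at Visits 1 and 3.

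SAP 5.2 sets two rules. For efficacy, "The nominal visit (ie, study visit captured on the CRF) will be used as the analysis visits in all efficacy analyses". For safety, a different rule holds: "For safety analyses, the unscheduled and Early Termination visits will be reclassified into analysis visits according to Table 2".

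The primary model in SAP 7.1.1 takes "visits (baseline and Week 40) as fixed effects", so it has no place for a third visit. SAP 5.3 rules out imputation. SAP 4.3 requires a valid baseline ECL value for the ITT set, but no later value.

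Two protocol passages bear on the label. Section 6.5 says "The Early Termination Visit CRF should be completed". Section 6.6 says that on discontinuation "the Investigator is expected to capture all the evaluations required at the end of study or follow-up".

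**The concern.** The SAP never names the optional biopsy, and the two protocol passages seem to point to different forms. Each label has a consequence that the SAP does not spell out.

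- **Labelled Early Termination.** The child stays in the ITT model with a baseline value only. SAP 7.1.3 adds a COVID-19 sensitivity analysis in which the study day of the Week 40 biopsy "will be added to the primary efficacy analysis model described in Section 7.1.1 (Primary Analysis) as a covariate". That day does not exist for this child, so the baseline row drops out, and the primary and sensitivity models no longer cover the same children.
- **Labelled Visit 3.** A biopsy from about day 182 counts as Week 40, because the efficacy rule has no lower time limit, although the endpoint is defined after 40 weeks of therapy.

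With only 15 to 20 children, one pair more or less is visible in the result. In an open-label, single-arm study, a choice made after the data are known would look discretionary.

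**Working it through.** **1. The passages side by side.** SAP 5.2 confines the reassignment of Early Termination visits to safety, so for efficacy they keep their own name. The protocol gives Early Termination its own schedule column and its own CRF (6.5). Section 6.6 says which evaluations to capture, not which visit label to enter. The Visit 3 column carries a window of Week 40 ± 14 days, and protocol 9.1.8 lists out-of-window visits as deviations. The natural label is therefore Early Termination, and such a biopsy does not enter a model whose visits are baseline and Week 40.

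**2. The plan's own sample size.** Inputs from SAP 3.3: baseline 0.2%, increase 0.08%, CV 30%, one-sided 5%, power 85%. Take a paired t-test on the log scale with effect ln(0.28/0.20) = ln 1.4 = 0.336 and SD of the difference √2 × 0.30 = 0.424. This gives N = 13, as stated. The same formula matches 11 of the 12 cells of SAP Table 1; the exception is 0.06% at CV 35% (27 against 28).

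**3. If the label is Early Termination.** One child of N has baseline only. Assume equal variances s² and a known correlation ρ between visits:

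- All pairs complete: Var = s² × 2(1−ρ)/N
- One baseline-only child: Var = s² × [(1−ρ²)/(N−1) + (1−ρ)²/N]

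For N = 15 and ρ = 0.5: 0.75/14 + 0.25/15 = 0.0702, against 1/15 = 0.0667. The variance ratio is 1.054.

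| N | ρ | Rise in variance | Rise in standard error |
|---|---|---|---|
| 15 | 0.5 | 5.4% | 2.6% |
| 15 | 0.8 | 6.4% | 3.2% |
| 20 | 0.5 | 4.0% | 2.0% |
| 20 | 0.8 | 4.7% | 2.3% |

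Power for the SAP example at N = 15 follows. SAP Section 10 gives a different significance level from 7.1.1, so 2.5% is shown as well, on the assumption that this is what Section 10 means.

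| Situation | One-sided 5% | One-sided 2.5% |
|---|---|---|
| 15 complete pairs | 0.899 | 0.815 |
| 14 pairs and one baseline-only child | 0.879 to 0.882 | 0.786 to 0.790 |
| 14 pairs, that child removed | 0.878 | 0.783 |

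The last two rows differ by less than 0.01. Losing the baseline row from the covariate model thus costs almost nothing, and the reported number of subjects would show it.

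**4. If the label is Visit 3.** If dystrophin does not change, an early biopsy also has an expected change of zero, so the false-positive rate is not raised. If the drug works, the early biopsy can only dilute, on two assumed patterns for one child of 15:

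- Response proportional to time, biopsy at day 182 of 280: that child shows 182/280 = 0.65 of the effect. The mean log change falls by 0.336 × 0.35/15 = 0.008, and the ratio goes from 1.400 to 1.389.
- No response at all: the mean log change is 0.336 × 14/15 = 0.314, a ratio of 1.369.

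**5. The planned check on timing.** The per-protocol set drops a child with "Week 40 visit not within 38 to 42 weeks from the Baseline visit". That is days 266 to 294, so a biopsy near day 182 is removed whatever its label.

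**The case for a change.** The best case for a change is that no visible sentence fixes the label, that one sentence would do so, and that the planned sensitivity analyses do not isolate this biopsy. Part of this stands. The text is silent, and adding the sentence would do no harm.

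The point about sensitivity analyses is partly right. The biopsy day takes one value per child and has no interaction with visit. In a model without muscle location and with complete pairs, adding it left the Week 40 estimate unchanged in simulation (largest difference 6e-16). The SAP model does include muscle location, and its primary value is the best across muscles, so location can differ between a child's two visits. With that term and assumed variances, the estimate moved by at most 0.025 to about 0.04 log units, with a median below 0.001. The covariate is thus a weak probe of an early biopsy, though not always an inert one.

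The per-protocol set does remove an early biopsy. It may also remove some of the 8 children whose Visit 3 was delayed by COVID-19 (SAP 5.6), so it does not isolate the effect. That loss comes from the delays, not from the optional biopsy.

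The worry about discretion carries little weight. A visit label is normally entered when the biopsy is taken. Under protocol 6.3 the samples are frozen, each child's pair is assayed together, and the assayers are blinded to timing. SAP 5.5 places all biopsies at one centre, which favours uniform labelling.

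**Conclusion.** No change follows. This is missing detail that an analyst fills correctly by applying SAP 5.2 as written: a biopsy recorded at an Early Termination visit is not a Week 40 value for efficacy. The eCRF completion guidelines cited in SAP Section 1 are the usual place for the label and may already fix it; they are not among the documents available.

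The cost per affected child is small. With 15 children it is a standard error 2.6% to 3.2% larger and about 2 to 3 points of power, which is what any missing Week 40 biopsy costs. Under the other label, the dilution is from 1.40 to no lower than about 1.37 on the patterns considered. Neither label undermines the primary test, provided that a missing Week 40 value is unrelated to the unseen result, as the observed-data approach already assumes.

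The figures rest on assumed correlations of 0.5 to 0.8, the SAP's example effect and CV, and one affected child. The documents do not say whether there was any.

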#### **5.6. COVID-19 Related Considerations**

Due to the Coronavirus Disease of 2019 (COVID-19) pandemic, 8 subjects will have Visit 3 (Week 40 visit) later than planned due to closure of the study site to study procedures. These subjects will receive continued therapy with ataluren until final study biopsies can be obtained. Since many subjects will have their Week 40 biopsy performed much later than after 40 weeks of ataluren treatment therapy, a sensitivity analysis will be conducted to include the Week 40 biopsy study day as a covariate in the analysis model. This sensitivity analysis will be performed for both the primary and secondary efficacy endpoints as detailed in Section 7.1.3 (Sensitivity Analyses) for the primary efficacy endpoint and in Section 7.2.2 (Sensitivity Analyses) for the secondary efficacy endpoint.

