## **8.2. Clinical Laboratory**

Clinical laboratory assessments for hematology, biochemistry, and urine evaluations are collected at Screening, Baseline and Week 40 visits. Mean and mean change from baseline for all hematology and biochemistry laboratory assessments, and continuous variables for urinalysis will be summarized using descriptive statistics at Baseline and Week 40 visits. Categorical variables for urinalysis will be tabulated using frequency count at Baseline and Week 40 visits. In addition, shift tables for each laboratory parameters from baseline to post-baseline visits will also be provided.

Creatine kinase, summarized as an efficacy endpoint, will be excluded from all laboratory summaries and listings.

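### SAP Table 2 gives unscheduled and early-termination safety results on days 2-70 no analysis visit, and its Week 40 rule lets an earlier unscheduled lab replace a delayed Visit 3 value

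*SAP*

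**What the plan says.** SAP 5.2 uses nominal visits for all efficacy analyses. Safety is treated differently: "For safety analyses, the unscheduled and Early Termination visits will be reclassified into analysis visits according to Table 2". The day count starts at first dose: "Study day 1 (baseline) is defined as the date of the first dose of study drug during the treatment period". Table 2 then sets target days 1, 140 and 280, with windows -45 to 1, 71 to 210, and 211 or later.

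Two rules settle competition within a window: "If multiple visits occurred within the same visit window, the one closest to the target visit date will be used in the analysis", and "If two visits are equidistant to the target visit date, the latest will be used". Neither distinguishes a scheduled visit from an unscheduled one.

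SAP 8.2 presents laboratory means and mean changes at two time points only; they "will be summarized using descriptive statistics at Baseline and Week 40 visits". It also promises shift tables from baseline to post-baseline visits, without restricting these to Week 40. SAP 5.3 rules out imputation.

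The Clinical Labs row of the protocol's schedule (Protocol 7.1, Table 1) marks Screening, Visit 1, Visit 3, unscheduled and early-termination visits, but not Visit 2. SAP 5.6 adds that "8 subjects will have Visit 3 (Week 40 visit) later than planned due to closure of the study site to study procedures", with ataluren continued until the final biopsy. The provisions that follow in SAP 5.6 concern only the primary and secondary efficacy endpoints.

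**The concern.** No laboratory draw is scheduled between Visit 1 and Visit 3. Any on-treatment lab in that interval is an unscheduled or early-termination result, which is exactly the kind that Table 2 has to place. For a child who stops early, the early-termination lab may be the only post-baseline value. The protocol foresees draws off the schedule: its renal monitoring table (Protocol 7.2, Table 2) calls for confirmation and work-up of abnormal values, and Protocol 6.4.2 requires repeated creatinine and BUN during certain antibiotic courses.

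If such results fall where no window exists, the by-visit tables omit them. If they fall in the Week 40 window of a child whose Visit 3 is late, they can push out the scheduled value. The Week 40 row would then mix scheduled end-of-treatment values with unscheduled values from other times, and nothing in the table would show it.

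**Working it through.** **Inputs.** Targets 1, 140 and 280, the window limits, and the closest-to-target and tie rules come from SAP 5.2 and Table 2. The laboratory summary time points come from SAP 8.2, the draw schedule from Protocol 7.1 Table 1, and the 8 delayed children from SAP 5.6.

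**Reproducing the limits.** They are midpoints between targets: (1 + 140)/2 = 70.5, so Week 20 starts on day 71; (140 + 280)/2 = 210, so Week 20 ends on day 210 and Week 40 starts on day 211. The baseline window was not extended to its own midpoint; it stops at day 1. That leaves the gap.

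**Where an off-schedule lab goes.** Days 2 to 280 are 279 days.

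| Study day | Days | Share of 279 | Analysis visit | Mean-change summary | Shift tables |
|---|---|---|---|---|---|
| 2-70 | 69 | 24.7% | none | no | no |
| 71-210 | 140 | 50.2% | Week 20 | no | can enter |
| 211-280 | 70 | 25.1% | Week 40 | yes, if selected | yes, if selected |

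Labs after day 280 also map to Week 40.

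**When an unscheduled lab displaces Visit 3.** Let Visit 3 fall on day D > 280. A lab on day d ≥ 211 is selected instead if |d - 280| < D - 280. For labs before Visit 3, this means d from max(211, 561 - D) to D - 1. A tie goes to the later visit, so Visit 3 survives a tie. The documents do not give the delayed dates, so every D beyond the protocol's +14-day limit (day 294) is an assumption.

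| Visit 3 on day D | Distance from 280 | Displacing days before Visit 3 | Share of days 211 to D - 1 |
|---|---|---|---|
| 294 | 14 | 267-293 (27 days) | 27/83 = 33% |
| 308 | 28 | 253-307 (55 days) | 55/97 = 57% |
| 330 | 50 | 231-329 (99 days) | 99/119 = 83% |
| 336 | 56 | 225-335 (111 days) | 111/125 = 89% |
| 350 | 70 | 211-349 (139 days) | 139/139 = 100% |
| 400 | 120 | 211-399 (189 days) | 189/189 = 100% |

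From day 350 onward, 561 - D is at or below 211, so any lab from day 211 to the day before Visit 3 displaces it. With Visit 3 on day 400, for example, a lab on day 215 is 65 days from target against 120 and becomes the Week 40 value.

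**The case against.** A reader might infer that early-termination labs as a group vanish from the safety tables, so that toxicity is hidden and the tables look cleaner than the data. The documents do not support that, for four reasons.

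- Only days 2-70 are lost from both kinds of laboratory table. Results on days 71-210 map to a post-baseline visit and can enter the shift tables. Results from day 211 stay in the Week 40 window.
- Adverse event summaries (SAP 8.1) do not use Table 2 and run to 6 weeks after the last dose. Under Protocol 7.3.1, a laboratory abnormality that needs intervention or further investigation is reported as an adverse event unless it belongs to an event already reported. SAP 8.2 also implies laboratory listings, since it excludes creatine kinase from them. With 15 to 20 children in one arm, listings and event tables should show a child who stops for toxicity.
- Displacement need not flatter the drug. An unscheduled lab drawn for cause could just as well put an abnormal value in place of a routine one.
- The open upper bound is what keeps a delayed Visit 3 in the Week 40 window at all, and a lab near day 280 is arguably closer to 40 weeks than one on day 400.

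These points limit the consequence but do not remove the defect. Abnormalities that need no intervention or further investigation are, by Protocol 7.3.1, left to laboratory monitoring, so the event tables will not show them. Listings do not repair a summary table. Whether the Week 40 row means nearest to 40 weeks or end of treatment is a legitimate choice, but the SAP should make it openly. At present the choice follows from a tie-breaking rule and from whether a child happened to have an extra draw.

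**Conclusion.** The point holds as a limited defect in the descriptive by-visit safety summaries. As written, the SAP places no off-schedule result from days 2-70, leaves those from days 71-210 out of the mean-change summary, and allows an earlier unscheduled lab to replace a late Visit 3 value. Vital signs taken at unscheduled visits fall under the same window rule.

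The shares above count calendar days, not children or results. The documents give no number of early terminations or unscheduled labs and no actual delayed visit dates, so the number of children affected cannot be computed and could be zero. Displacement requires an unscheduled result after day 210 in a child whose Visit 3 is further from day 280. The SAP names 8 delayed children against 15 to 20 planned (8/20 = 40% to 8/15 = 53%), so the conditions for it are not rare. With so few children, one lost or replaced value can change a shift table. Adverse event tables are unaffected, and the efficacy analyses use nominal visits and are untouched.

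**What to change.** - **SAP 5.2:** state that a scheduled Visit 3 result takes priority over unscheduled results in the Week 40 window. The closest-to-target rule then applies only where no scheduled Visit 3 result exists for that parameter.
- **SAP 8.2:** add a shift table from baseline to the worst post-baseline value, using all scheduled, unscheduled and early-termination results from day 2 onward (after first dose), regardless of visit window. Define the direction of worst for parameters with both a low and a high limit.

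Moving the start of the Visit 2 window to day 2 is not a good substitute. It would label a day-3 lab as Week 20 and would restore nothing to the mean-change summary, which has no Week 20 row. The cost of the two changes is minor programming and one extra table.
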